5.1.2.6 Conclusion of sample size estimation

Based on these results we assume that we will likely be able to stop collecting data before reaching **75 patients per arm (total of 150 patients) to reach a BF of 10**. We aim to collect a minimum of 40 patients per study arm. From that point on, we will perform the abovementioned BF test after every 40 new patients (about 20 per arm, exact number subject to randomization). The evidence is regularly calculated until either a pre-set level of evidence threshold is achieved in favor of either of the hypotheses (BF of 10 or 1/10 respectively, considered as strong evidence), or when the maximum sample size is reached. For the current study, we chose to set the maximum total sample size at 200 (as deemed sufficient based on a frequentist sample size estimation for the same assumptions). If this threshold is not reached, a new cost-benefit analysis of continuing to collect data will be performed. However, as described above, this is highly unlikely. After data collection is deemed completed and follow-ups at 6 months are complete, all secondary and sensitivity analyses will be performed. For the data collected up to 40 per arm, a p-value may be calculated (sensitivity analysis) and used for a classical hypothesis test.

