5.1.2.3 Bayesian A/B Test

We calculated the BF using the method presented by Gronau et al.[53] as implemented in the R package `ab_test`. For these first exploratory simulations, we used the default parameter priors supplied by the R package. The Bayes Factor calculated in this way, quantifies how much more likely the data originate from a “truth” where the probability in both arms is equal, vs a truth where both probabilities are different.

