5.1.2.5 Sample size analysis results

Figure 3 shows the results of a simulation, in which for various proportions of positive outcome for BMT (0.4, 0.5, 0.6, different panels) and various assumed positive risk ratios in favor of ES over BMT (1.2, 1.3, 1.4, 1.5, 1.6, differently colored lines), a large number of hypothetical trials were simulated, collecting up to 170 observations per study arm. The lines indicate the proportion of such simulated trials that reached the BF threshold of 10 in favor of either the null or the alternative hypothesis at each sample size.

Comparing the panels, one can see that, the higher the probability in the control arm, the quicker the percentage of trials that achieved the BF-threshold rises. In other words: the higher the baseline proportion of good outcome in the BMT arm, the lower the expected sample size. Comparing differently colored lines within panels, one can see that with higher risk ratios, the expected n decreases.

Systematic reviews as well as data analyzed from the Swiss Stroke Registry over the last 2 years suggests that a plausible assumption for the proportion of positive outcomes in the control arm is 50% (0.5) (Figure 2b). The pink line indicates the anticipated risk ratio of 1.6 in favor of ES. Based on our calculations after collecting data of 70 patients per study arm, about 90% of trials will have achieved a BF of 10, being the “Bayesian equivalent” to a power of 90%. In addition, 50% of the simulated trials already achieve this level of evidence after the 40th hypothetical patient (per arm). Further, based on these calculation, it is extremely unlikely that the trial would take more than 130 patients per arm. Based on these results we assume that we will likely be able to stop collecting data before reaching **75 patients per arm (total of 150 patients) to reach a BF of 10.**

[figure not shown]

Figure 3: Results of the simulation for SSE at different probabilities and Risk Ratios. A) For a probability of favorable outcome in BMT of 40%; B) for a probability of 50% and C) for a probability of 60%

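### The quoted 90% chance of reaching a Bayes factor of 10 by 70 per arm fits near-continuous monitoring; the scheduled looks give about 80% before 75 per arm

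*Protocol*

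**What the plan says.** - **Simulation.** Section 5.1.2.2 says the sample size analysis exploits the freedom to check the accumulating data at any moment. Section 5.1.2.5 describes curves of the proportion of simulated trials that reached the threshold at each sample size. For a 50% control rate and a risk ratio of 1.6 it states: "Based on our calculations after collecting data of 70 patients per study arm, about 90% of trials will have achieved a BF of 10". It presents this as the Bayesian counterpart of 90% power, and adds that half the trials are there by 40 per arm and that going beyond 130 per arm is extremely unlikely.
- **Conclusion.** Sections 5.1.2.5 and 5.1.2.6 infer from these results that data collection will likely stop before "75 patients per arm (total of 150 patients) to reach a BF of 10". The synopsis repeats both figures as the rationale for the number of participants.
- **Schedule.** Section 5.1.2.6: "We aim to collect a minimum of 40 patients per study arm". After that, "we will perform the abovementioned BF test after every 40 new patients", about 20 per arm, up to a maximum of 200 in total. Section 5.1.3 repeats the 40-patient interval. Section 5.1.4 allows inspection at any time but again plans the primary analyses every 40 patients.

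**The concern.** The simulation and the schedule appear to describe two different monitoring plans. If a simulated trial is credited with success whenever it crosses the threshold at any sample size, the resulting curve belongs to a trial that looks almost continuously. The scheduled tests fall at about 80, 120, 160 and 200 patients. On that schedule, stopping before 75 per arm means having stopped by the 60-per-arm look, and no figure is given for that.

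At stake is whether the power-type figure in the synopsis describes the trial as scheduled. Ethics reviewers, the funder and the data and safety monitoring board would naturally read the 90% and the 150 patients that way. The enrolment ceiling, the evidence threshold and the analysis method are not affected.

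**Working it through.** **Inputs**
- Control rate 0.50 (section 5.1.2.5).
- Effect: "The pink line indicates the anticipated risk ratio of 1.6 in favor of ES" (section 5.1.2.5), so the surgery rate is 1.6 × 0.50 = 0.80.
- Allocation 1:1 (section 3.3.3).
- Stop at a Bayes factor of at least 10 or at most 1/10 (section 5.1.2.6).
- Two-sided comparison: equal probabilities "vs a truth where both probabilities are different" (section 5.1.2.3).
- Priors: "we used the default parameter priors supplied by the R package" (section 5.1.2.3). Their values are not printed. **Assumption:** standard normal on the mean log-odds β and on the log odds ratio ψ; varied in step 3.

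**Model.** logit p(BMT) = β − ψ/2 and logit p(ES) = β + ψ/2. With n per arm and y0, y1 good outcomes,

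BF10 = ∫∫ Bin(y0; n, p(BMT)) Bin(y1; n, p(ES)) φ(β) φ(ψ) dβ dψ ÷ ∫ Bin(y0; n, p) Bin(y1; n, p) φ(β) dβ, where logit p = β in the denominator.

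BF10 was computed by numerical integration for every possible (y0, y1). An exact forward recursion at 0.50 versus 0.80 then gave the cumulative probability of having stopped. At these rates, essentially all stopping is at the upper threshold.

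**Step 1: reproduce the stated figure.**

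| Look pattern | Reached by 40 per arm | Reached by 70 per arm |
|---|---|---|
| After every pair of patients | 63.8% | 90.5% |
| Every pair, starting at 40 per arm | 55.0% | 89.9% |
| Every 5 per arm | 60.3% | 89.3% |
| Every 10 per arm | 58.4% | 88.4% |
| One look only, at that size | 55.0% | 85.7% |
| **Protocol states** | **50%** | **about 90%** |

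Looks after every pair also give 92.2% by 74 and 99.6% by 130 per arm, which agrees with the statement about 130. Frequent looking therefore reproduces the 90%; a single look at 70 falls short of it. The stated 50% by 40 per arm is not reproduced exactly by any pattern. With looks after every pair, 50% is reached at about 32 per arm.

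**Step 2: the scheduled looks.**

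| Look (per arm) | Evaluated patients | Cumulative stopped | Stopped at this look |
|---|---|---|---|
| 40 | 80 | 55.0% | 55.0% |
| 60 | 120 | 79.8% | 24.8% |
| 80 | 160 | 92.0% | 12.2% |
| 100 | 200 | 97.0% | 5.0% |

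The last look before 75 per arm is at 60, so the chance of stopping before 75 is 79.8%. The shortfall is 90 − 79.8 = 10.2 points against the quoted figure, and 92.2 − 79.8 = 12.4 points against every-pair looks carried to 74 per arm. An extra look at 20 per arm changes 79.8% only to 80.2%. A simulation of 40,000 trials with permuted blocks, where arm sizes are not exactly equal at a look, gives 79.7%.

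**Step 3: sensitivity to the priors.** With the SD of ψ from 0.5 to 2 and of β at 1 or 2:
- looks after every pair, by 70 per arm: 85% to 91%;
- scheduled looks, before 75 per arm: 71% to 80%;
- difference between these two: 11 to 14 points throughout;
- scheduled looks by 80 per arm: 89% to 92%; by 100 per arm: 96% to 97%.

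**Step 4: adding a look at 75 per arm** to the schedule gives 90.1% cumulatively at that look under standard normal priors (86% to 90% over the same prior range).

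**The case against.** The strongest reply is that the protocol reserves the right to look at any time (section 5.1.4), describes exactly that in 5.1.2.2, and ties the 90% to simulated trials at 70 per arm rather than to the scheduled tests. The sentence about 75 per arm says only that stopping is likely, and 80% is still likely. This much stands: the sentence is not false as worded. The permission to inspect does not supply a figure for the schedule, however, and the schedule is stated three times as every 40 patients.

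Three stronger readings are tempting and are not supported:
- *That the 90% holds only with a look at every patient.* Looks every 5 or 10 per arm still give 89% and 88% by 70 per arm.
- *That the trial cannot stop at 75 per arm.* It is not a scheduled look, but section 5.1.4 leaves unscheduled inspection open and interval sizes are approximate.
- *That 150 is an expected sample size that is now too low.* The protocol gives it as a size the trial will probably stop before. On the scheduled looks the mean, counting trials still undecided at the maximum as 200, is 0.550 × 80 + 0.248 × 120 + 0.122 × 160 + 0.080 × 200 = 109 evaluated patients.

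It is also fair to say that the simulation's counting rule is inferred, that its figure is not available here, that the printed 50% by 40 per arm is not matched, and that the priors are assumed. These limit confidence in the exact percentages, but the gap persists across all priors tried.

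**Conclusion.** The point holds as a mismatch between a stated operating characteristic and the scheduled design. The quoted 90% by 70 per arm is what near-continuous monitoring delivers. The schedule delivers about 80% before 75 per arm (71% to 80% over the priors tried), about 10 points less. Under standard normal priors, 90% is first passed at 160 evaluated patients (about 92%); with the narrowest or widest priors tried, that look gives 89% to 90%.

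The consequence is moderate. About 97% of trials reach the threshold by the 200-patient maximum, so a reader should not infer that the trial is underpowered on its own assumptions. All figures rest on 50% versus 80%, a two-sided Bayes factor and the assumed priors. They count patients with a 6-month outcome; the number enrolled at each look will be larger unless recruitment pauses.

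**What to change.** The sponsor should rerun its own simulation, with the priors it actually used, at looks of 40, 60, 80 and 100 per arm. It should then restate the figures in the synopsis, 5.1.2.5 and 5.1.2.6, saying which look schedule they belong to. Expected values are about 55% by 80, 80% by 120, 92% by 160 and 97% by 200 evaluated patients. These should come from the sponsor's rerun rather than be copied from here, because they depend on priors the protocol does not print.

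Alternatively, add a scheduled look at 75 per arm (about 90% cumulatively) and quote that figure.

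The first option is a simulation rerun and a text change; the second also adds one interim test. With the first, the stated figure becomes slightly less favourable. Neither changes the 200-patient ceiling or the threshold.

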5.1.2.2 Bayesian Sequential analysis

Based on the to-date available literature[19, 23, 24], our own meta-analysis and the data of 2020-2022 derived from the Swiss stroke registry we assume a favorable outcome around 50% for patients treated with BMT, while we anticipate a positive risk ratio of 1.6 towards favorable outcome for ES compared to BMT. Based on these assumptions, we explored sample sizes needed for achieving “compelling evidence”, as described by Schönbrodt & Wagenmakers[51]. Compelling evidence is defined as finding a Bayes Factor (BF) that points with a certain strength at favoring the null hypothesis or the alternative hypothesis i.e. hypothetical experiments, expressing how much more likely the data were generated from a model where both study arms have the same probability of a positive outcome, compared to a model where there is a difference in the probability of a positive outcome. Simply put, it essentially measures the evidence between the two hypothesis. The BF expresses how likely the data originates from one hypothesis vs. the other (For an introduction into the interpretation of Bayes Factors as indices of evidence, please refer to Jarosz & Wiley[52]). Often used verbal interpretations are “substantial” or “positive” for BFs around 10, and “strong” to “very strong” for BFs over 100. Of all the strengths when using BF as opposed to p-values for inference, two stand out:

- A BF may quantify evidence against or in favor of the null-hypothesis.
- BFs may be monitored continuously as the data is generated and collected without the need of correction schemes as needed in a classical null-hypothesis significance testing procedures.

Both strengths described above are exploited in the sample size analysis performed here: we peak at the data at any moment to see whether we have enough evidence, to allow to decide in favor of either the alternative, or the null hypothesis. Note that it does not make sense to additionally calculate a p-value at the finally achieved n. Such a p-value will, by nature, be biased towards “significance”.

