5.1.3 Planned statistical methods

The primary analyses are performed following the intention-to-treat principle. Additionally, per-protocol analysis will be performed for sensitivity analysis. We study the ratio of positive outcomes in both study arms by performing a Bayesian A/B test after every 40 additional patients, using the method described by Gronau et al.[53]. Data collection (and the periodical analysis of these data) will continue until a Bayes Factor of 10 (or 1/10) is achieved. The odds

ratio and its 95% credible interval will be reported. Covariates ICH volume, presence of intraventricular bleeding, do-not-resuscitate orders, location of hematoma and centre will be included in a Bayesian logistic regression model

Secondary analysis is performed on the secondary outcomes. For continuous variables, a Bayesian regression with normal error term is used, for time-to-event outcomes Bayesian cox-regression is used, and for binary variables Bayesian logistic regression is used. Statistical analysis is performed with R version 4.2.1 or higher (R core Team, 2022)[54]. A complete mRS shift analysis will be calculated.

In parallel to the Bayesian primary analysis, we will perform a frequentist test of proportions comparing study arm for the first 100 patients per study arm. In the ES arm, a number of explorative analyses are performed, studying the relation between hematoma location, hematoma size, and treatment outcome. In particular, for parameters measured over time, figures are created illustrating the development over time at both the patient level and group level.

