5.1.4 Interim analysis

As described under “5.1.2.6. Conclusion of sample size estimation”, the data may be inspected any time, but we plan to perform the primary analyses after every 40 patients (20 per arm), and will stop data collection if the BF, in favor of either the null, or the alternative hypothesis is over 10.

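### Within 200 patients the Bayes factor threshold for the null (1/10) is out of reach for any zero-centred normal log-OR prior with SD below about 2.8, and ending undecided is common unless the effect is close to the planned one

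*Protocol*

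**What the plan says.** The primary analysis is a Bayesian A/B test comparing equal with different good-outcome rates; the hypotheses in 5.1.1 are two-sided. Section 5.1.2.2 lists as a strength that "A BF may quantify evidence against or in favor of the null-hypothesis" and says the design uses it. Section 5.1.2.4 caps the total at 200. Section 5.1.2.6 plans a first test at 40 per arm, then one after every 40 further patients, stopping at a "BF of 10 or 1/10 respectively, considered as strong evidence), or when the maximum sample size is reached". If no threshold is met at 200, a cost-benefit review of continuing follows, and the section describes that situation as very improbable. Section 5.1.4 says the trial "will stop data collection if the BF, in favor of either the null, or the alternative hypothesis is over 10".

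Section 5.1.3 and the synopsis (Statistical Considerations) repeat the rule without the cap: data collection "will continue until a Bayes Factor of 10 (or 1/10) is achieved". Section 7.1 adds a different rule: premature termination if ES shows no significant effect at the interim analysis.

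On the prior, 5.1.2.3 says only that "we used the default parameter priors supplied by the R package", and describes those simulations as exploratory. The scenarios in 5.1.2.5 are "various assumed positive risk ratios in favor of ES over BMT (1.2, 1.3, 1.4, 1.5, 1.6, differently colored lines"). There is no risk ratio 1.0 scenario, and the figure counts trials reaching either boundary together.

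**The concern.** Evidence for a point null builds slowly. When the prior under the alternative is centred on no effect, even identical results in both arms raise the Bayes factor for the null (BF01) only roughly as the square root of the sample size. A threshold that is symmetric on paper may therefore be reachable only on the alternative side. If so, the ethics committee and the data monitoring committee are told of a stop for no difference that cannot occur, and the stated chance of ending undecided is wrong in the scenarios where ES has no effect or a modest one.

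**Working it through.** **Inputs from the protocol.** Control rate 0.50 (5.1.2.5); risk ratio 1.6, so ES 0.80 and OR (0.8/0.2)/(0.5/0.5) = 4.0 (5.1.2.2); 1:1 allocation (3.3.3); looks at 40, 60, 80 and 100 per arm, thresholds 10 and 1/10, maximum 200 (5.1.2.4, 5.1.2.6).

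**Assumption.** Logit rates are β ∓ ψ/2, with β ~ N(0,1). ψ, the log odds ratio, is N(0, s²) under H1 and 0 under H0. The protocol does not give s, so it is varied. The Bayes factor was integrated numerically.

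**Reproducing the plan's figures (s = 1, 0.50 vs 0.80).** By 70 per arm 90.4% of simulated trials reach BF 10 under continuous monitoring (stated: about 90%). By 40 per arm it is 55% at a single look and 64% under continuous monitoring (stated: 50%). By 130 per arm it is 99.6%. No trial crossed on the null side, so the 90% comes entirely from the alternative side.

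**Largest possible BF01.** At p = 0.5 the variance of the log odds ratio is 8/n, with n per arm. With identical arms, BF01 ≈ √(1 + s²·n/8). For s = 1 and n = 100 this is √13.5 = 3.67. Exact integration, searched over every pair of event counts, gives 2.43, 2.90, 3.30 and 3.66 at 40, 60, 80 and 100 per arm, and 4.71 at 170 per arm, where the protocol's simulation ends. Reaching 10 at 100 per arm needs s² = 99 × 8/100 = 7.92, so s ≈ 2.8.

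| Prior SD of log OR | Max BF01 at 100 per arm |
|---|---|
| 0.5 | 2.0 |
| 1 | 3.7 |
| 1.5 | 5.4 |
| 2 | 7.1 |
| 2.5 | 8.9 |
| 2.8 | 9.9 |
| 3 | 10.6 |

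Changing the SD of β from 0.5 to 5 leaves 3.66 unchanged to two decimals; an 80:120 split gives 3.59. Independent uniform priors on the two rates give 5.7 at 50%, and pass 10 only when both arms have about 8% or fewer, or 92% or more, good outcomes.

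**Trials ending at 200 with neither threshold met (exact recursion over the four looks).**

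| True rates | RR | s = 1 | s = 0.5 to 2.5 |
|---|---|---|---|
| 0.50 / 0.50 | 1.0 | 98.4% | 98-99% |
| 0.50 / 0.60 | 1.2 | 87% | 87-91% |
| 0.50 / 0.65 | 1.3 | 68% | 68-74% |
| 0.50 / 0.70 | 1.4 | 40% | |
| 0.50 / 0.75 | 1.5 | 15% | |
| 0.50 / 0.80 | 1.6 | 3% | |

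At s = 1 with no difference, the remaining 1.6% wrongly reach BF 10 and 0% reach 1/10. At s = 3 about 28% of no-difference trials cross 1/10 and just over 71% end undecided.

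**The case against.** **The prior is not given.** The strongest objection is that unreachability depends on values absent from the protocol. This stands as a condition: at SD 3 the null threshold can be crossed. Nor does matching the stated 90% at 70 per arm single out SD 1. With checks every 5 patients per arm the figure moves only from 89% (SD 1) to 85% (SD 3), and the stated 50% at 40 per arm fits SD 2.5 or 3 at a single look (50%) better than SD 1 (55%). So 3.7 is one value in a range. However, the exception needs a very wide prior: at SD 2.8, 95% of its weight lies between odds ratios of about 1/242 and 242 (e^(1.96 × 2.8) ≈ 242), against a planned 4.0.

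**A one-sided Bayes factor.** The protocol does not specify one. It could cross 1/10 by 200 patients only when ES looks worse (3.3% of no-difference trials at SD 1); equal arms still give 3.66.

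**Stronger readings.** From 5.1.3 alone a reader might infer a trial with no practical end if ES does nothing: at SD 1 the earliest null stop would be about 800 per arm. The document as a whole does not support this, because 5.1.2.4 and 5.1.2.6 state a maximum of 200, although reaching it only triggers a decision on continuing. A reader might also infer that the trial could not stop early without an effect; section 7.1 gives a separate termination rule, and 6.7 allows termination on other grounds.

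**The trial remains interpretable.** Section 5.1.3 already reports the odds ratio with a 95% credible interval, so a trial without a crossing still yields an estimate. That is correct, but it does not repair the stopping claim.

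**Conclusion.** The concern holds, conditionally on the prior. For a two-sided Bayes factor, rates near 50% and a zero-centred normal log-OR prior with SD below about 2.8, the 1/10 threshold cannot be reached within 200 patients. It should not stand as a stopping rule or a claimed strength unless the analysis prior is shown to make it reachable.

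Independently of the exact prior, the statement that ending without a threshold is very improbable holds only near risk ratio 1.6. Two of the protocol's own scenarios, risk ratios 1.2 and 1.3, end that way in most trials, and a no-difference trial does so in about 98-99% of cases for SD 0.5 to 2.5. The stopping rules in 5.1.2.4 and 5.1.2.6, in 5.1.3 and the synopsis, and in 7.1 do not agree. The documents do not support the unconditional claim that the trial can never favour the null.

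**What to change.** 1. State the prior for the primary analysis with its values, and report operating characteristics at risk ratio 1.0 with the two boundaries shown separately.
2. If 1/10 is unreachable within 200 under that prior, say so and remove it as a stopping rule and as a claim in 5.1.2.4, 5.1.2.6, 5.1.3, 5.1.4 and the synopsis.
3. In 5.1.2.6, replace the statement about ending without a threshold with the computed probabilities for risk ratios 1.0 to 1.6.
4. Reconcile the uncapped rule in 5.1.3 and the synopsis with the 200 maximum in 5.1.2.4 and 5.1.2.6 and with the termination rule in 7.1.
5. State that if 200 is reached without a crossing, the odds ratio, 95% credible interval and Bayes factor are reported as inconclusive.

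A lower null threshold is the sponsor's choice, to be made from simulations under the stated prior. No value is recommended here because the error rate depends heavily on that prior: with BF01 ≥ 3, a false null stop at a true OR of 2 occurs in 0% of trials at SD 0.5, 5% at SD 1 and 36% at SD 2.

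The cost is a short simulation and some rewording, and the protocol's stated properties become less favourable.
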